8.2.5 Pharmacokinetic analysis set

The PK analysis set will include all patients who receive the AZD1775 dose and provide at least one PK sample.

If a patient has a major protocol deviation that affects the evaluability of the PK profile, then the patient will not form part of the PK analysis set.

Major protocol deviations include changes to the procedures that may impact the quality of the data or any circumstances that can alter the evaluation of the PK. Examples include, but may not be limited to: vomiting following oral dosing occurring within the time frame of 2 times the median t_{max} , sample processing errors that lead to inaccurate bioanalytical results, incomplete dose administered, incomplete PK profile collected, and/or use of disallowed concomitant medication. In the case of a major protocol deviation, affected PK data collected will be excluded from the summaries and statistical analyses, but will still be reported in the study result listings. Major deviations will be listed and summarised in the CSR.

8.2.6 Pharmacokinetic analysis set

The PK analysis set will include all patients who receive the AZD1775 dose and have full PK sampling up to 10 hours post-dose.

If a patient has a major protocol deviation that affects the evaluability of the PK profile, then the patient will not form part of the PK analysis set.

Major protocol deviations include changes to the procedures that may impact the quality of the data, or any circumstances that can alter the evaluation of the PK. Examples include, but may not be limited to: vomiting following oral dosing occurring within the time frame of 2 times the median t_{max} , sample processing errors that lead to inaccurate bioanalytical results, incomplete dose administered, incomplete PK profile collected, and/or use of disallowed concomitant medication. In the case of a major protocol deviation, affected PK data collected will be excluded from the summaries and statistical analyses, but will still be reported in the study result listings. Major deviations will be listed and summarised in the CSR.

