- r Optional whole blood PGx samples (10 mL) will be taken pre-dose on Cycle 1 Day 1 (see Section 5.6.2). If for any reason the sample is not drawn at Cycle 1 Day 1, it may be taken at any visit until the last study visit. Only one sample should be collected per subject for genetics during the study. This sample is **optional** and must be taken from patients who have provided informed consent for genetic sampling and analysis.
- s Optional tumour biopsies (from the primary tumour or metastatic site) will be collected from consenting patients with easily accessible tumours (see Section 5.5.5). Tumour samples may be collected at screening or baseline before dosing and at the time of disease progression. This sample is **optional** and must be taken from patients who have provided informed consent for tumour biopsies. All tumour biopsies will be collected, stored and shipped as detailed in the Investigator Laboratory Manual.
- t PK collections during safety lead-in patients Cycle 1 Day 1 and steady state collections on Cycle 1 Day 3 or Day 10 (see Section 5.3.1). Sample collected from time (h) \pm 15 minutes post-AZD1775 dose: pre-dose, 1h, 2, 4, 6, 8 and 12h post dose. Details for processing, handling, and shipping are in the Laboratory Manual.
- u AZD1775 (200 mg PO) BID Days 1-3 and 8-10 of each treatment cycle. AZD1775 should be taken with 8 ounces of water approximately 2 hours before or 2 hours after food. Note: the AZD1775 BID starting dose is reduced to 175 mg (Days 1-3, week 1 and week 2 of each 21-day cycle) because 200 mg BID was not well-tolerated.
- v Dispense AZD1775 at the beginning of each new treatment cycle, and review and document AZD1775 dosing compliance with the patient at each visit.
- w When applicable, tumour markers that are elevated and are used by the Investigator to monitor for tumour response will be collected at baseline, Day 1 of each cycle and at the end of treatment. The tumour marker analysis will be performed by a local laboratory.
- x Previous individual patient genomic profile reports should be provided for this study at baseline or screening.

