5.3 Pharmacokinetics

5.3.1 Collection of blood pharmacokinetic samples during safety lead-in (Part A only – closed to enrolment October 2015)

Pharmacokinetic (PK) samples will be collected during the safety lead-in portion of the study during Cycle 1 Day 1 and Cycle 1 Day 3 or Day 10. Steady state PK collections may occur on Day 3 or Day 10 of Cycle 1. The Investigator may select the PK collection day that fits best for the clinic and the patient for the second set of PKs. The date and actual time of the PK sample will be recorded.

Table 4 Cycle 1 Day 1 and Cycle 1 Day 3 or Day 10 safety lead-in PK collections

Time (h) post first AZD1775 dose	0	1	2	4	6	8	12
Swallow AZD1775	X						
PK Sample	X ^a	X ^b	X ^c	X ^c	X ^c	X ^c	X ^c

^a PK sample may be collected the day before dosing.

^b ±5 minutes.

^c ±15 minutes

The timing of the PK samples may be adjusted during the study, dependent on emerging data, in order to ensure appropriate characterisation of the plasma concentration-time profiles.

If a patient misses any doses of AZD1775 a day prior to PK sampling, the Medical Monitor should be contacted regarding the changes required for the timing of the PK assessments. All other assessments, including laboratory safety assessments, vital signs and RECIST should continue to be performed as per study plan, relative to baseline assessments.

Details on sample processing, handling, and shipment are provided in the Laboratory Manual.

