5.3.2 Collection of blood pharmacokinetic samples during Part B expansion

PK blood samples will be required from all patients enrolled at approximately 3-5 investigational sites to ensure we have evaluable data from at least 50 patients. These required samples may become optional once there are samples from at least 50 patients. PK blood sampling is highly recommended for all patients at the remaining sites. PK blood sample collections will be taken from consenting patients pre-dose and 2-4 hours post-dose on Day 3 or Day 10 of Cycle 1, Cycle 2, and Cycle 4, and beyond Cycle 4 every 2 cycles. The date and actual time of all PK samples must be recorded.

Table 5 Part B PK collections

Cycle 1, 2, and 4 (and beyond cycle 4 every 2 cycles) Day 3 or Day 10		
Time (h) post first AZD1775 dose	0	2-4 hours
Swallow AZD1775	X	
PK Sample ^a	X	X

^a ±15 minutes

Details on sample processing, handling, and shipment are provided in the Laboratory Manual.

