8.8 Calculation or derivation of pharmacokinetic variables

Pharmacokinetic analysis of plasma for AZD1775 concentration data will be performed by Covance on behalf of AstraZeneca. The actual sampling times will be used in the parameter calculations and PK parameters will be derived using standard non-compartmental methods

Where possible the following PK parameters will be determined for AZD1775

- C_{\max}
- C8hr
- Time to C_{\max} (t_{\max})
- Time of last detectable concentration (t_{last})
- Terminal half-life ($t_{1/2\lambda z}$)
- Area under the plasma concentration-time curve from zero to 8 hours ($AUC_{(0-8)}$), from zero to the time of the last measurable concentration ($AUC_{(0-t)}$), and from zero to 12 h ($AUC_{(0-12)}$).

Following the multiple dose part of the study (Day 3 or Day 10) the following additional parameters will be calculated

- Accumulation on day 3 or 10 compared to day 1 for C_{\max} and $AUC_{(0-12)}$
- C_{trough}

The C_{\max} and t_{\max} parameters will be determined by inspection of the concentration time profiles. Where possible the terminal elimination rate constant (λz) will be calculated by log-linear regression of the terminal portion of the concentration-time profiles where there are sufficient data and the terminal (elimination) half-life ($t_{1/2\lambda z}$) will be calculated as $\ln 2/\lambda z$. The area under the concentration-time curve up to the last quantifiable sample ($AUC_{[0-t]}$) and the $AUC_{(0-8)}$ will be calculated using the linear up, log down trapezoidal rule. Where appropriate, the $AUC_{(0-t)}$ will be extrapolated to infinity using λz to obtain AUC. The area under the concentration-time curve across the dosing interval, AUC_{ss} will be calculated using the linear

up, log down trapezoidal rule. The apparent clearance (CL/F following the single dose and CL_{ss}/F following multiple dosing) will be determined from the ratio of dose/AUC or dose/ AUC_{ss} . The volume of distribution (V_{ss} , V_{ss}/F or V_z/F) will be determined from the $MRT \times CL/F$ and/or the accumulation ratio (RAC) will be calculated as the ratio of the $AUC_{(0-8)}$ on Cycle 3 Day 1. The time dependency of the pharmacokinetics on multiple dosing will be assessed by the calculation of the ratio of $AUC_{(ss)}/AUC(\text{single dose})$.

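### The PK analysis set has two incompatible definitions, one of which no Part B patient can meet on its plain reading, and the accumulation ratio is tied to a day with no PK sampling

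*Protocol*

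**What the plan says.** Two consecutive sections of the protocol carry the same title. Section 8.2.5 reads: "The PK analysis set will include all patients who receive the AZD1775 dose and provide at least one PK sample". Section 8.2.6 reads: "The PK analysis set will include all patients who receive the AZD1775 dose and have full PK sampling up to 10 hours post-dose". Neither is limited to Part A or Part B, and no rule of precedence is given. Both then repeat nearly the same text on major deviations, in which an incomplete PK profile is one example.

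The sampling plans differ by part. In Part A, Section 5.3.1 collects samples "during Cycle 1 Day 1 and Cycle 1 Day 3 or Day 10", and the PK footnote to Table 1 sets the times as "pre-dose, 1h, 2, 4, 6, 8 and 12h post dose". In Part B, Section 5.3.2 takes samples "pre-dose and 2-4 hours post-dose on Day 3 or Day 10 of Cycle 1, Cycle 2, and Cycle 4", then every second cycle. Its stated aim is "to ensure we have evaluable data from at least 50 patients".

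Section 8.8 treats accumulation in two places. Its list of multiple-dose parameters compares Day 3 or 10 with Day 1 for Cmax and AUC(0-12). Its closing text says "the accumulation ratio (RAC) will be calculated as the ratio of the" AUC(0-8) on Cycle 3 Day 1, and stops there without naming the other term of the ratio.

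Characterising the PK profile is a secondary objective in both parts (Section 2.2).

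**The concern.** A single named analysis set must have a single membership rule. Here a later document that refers to the PK analysis set has to depart from one of two current sections. The choice is not cosmetic, because the two rules give opposite answers for Part B: one can admit everyone sampled, the other nobody on its plain reading. If it is left open until the data are in hand, set membership is decided after the fact.

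The accumulation sentence is a separate fault of the same kind. It prescribes a calculation from a day on which no PK sample is scheduled, and it competes with another definition in the same section.

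**Working it through.** The plan gives no figure to reproduce here. The check sets each rule against the sampling schedule.

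**Inputs**

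- Part A times (Table 1 PK footnote, Table 4): 0, 1, 2, 4, 6, 8 and 12 h. Days (Section 5.3.1): Cycle 1 Day 1, and Cycle 1 Day 3 or 10.
- Part B times (Section 5.3.2, Table 5): pre-dose and 2-4 h, each within 15 minutes. Days: Day 3 or 10 of Cycles 1, 2 and 4, then of every second cycle.
- Entry rules: one or more samples (8.2.5); a full profile to 10 h (8.2.6).

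**Part B against 8.2.6.** Latest scheduled sample = 4 h + 0.25 h = 4.25 h, which is less than 10 h. Qualifying patients: 0 of the targeted 50 or more.

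**Part B against 8.2.5.** One sample is enough, so all 50 or more can enter, subject to the major-deviation exclusion.

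**Part A against 8.2.6.** The last time at or before 10 h is 8 h and the next is 12 h. A complete Part A profile spans 10 h, so Part A patients can qualify. With no sample at 10 h itself, the rule leaves open whether the 12 h sample is required.

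**Accumulation on Cycle 3 Day 1**

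- Part A PK days are all in Cycle 1, so Cycle 3 is never sampled.
- Part B PK days are Day 3 or 10 of Cycles 1, 2, 4, 6 and so on, so neither Cycle 3 nor any Day 1 is sampled.
- Part B could not give a non-compartmental AUC(0-8) at any visit, since 4.25 h is less than 8 h.
- The denominator is not stated.

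**Accumulation as Day 3 or 10 against Day 1.** AUC(0-12) needs a 0-12 h profile on both days. Part A schedules both, so the ratio can be computed there. Part B has neither profile.

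**Would adding a Cycle 3 Day 1 sample help?** Section 7.2 puts dosing on Days 1-3 and 8-10 of a 21-day cycle, so Days 11-21 are drug-free: 11 × 24 h = 264 h. With the half-life of about 10 h in Section 1.1.3, that is 264 / 10 ≈ 26 half-lives. The first dose of Cycle 3 would look like a single dose and show no accumulation. This assumes that the single-dose half-life holds on repeat dosing.

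**The case against.** The strongest defence is that little depends on this. PK is secondary and descriptive, there is no hypothesis test, and a fuller analysis plan is due before database lock. That stands, and it limits the weight of the point. It does not remove a contradiction that the protocol itself states.

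A second defence is that full sampling could mean every sample scheduled within the first 10 h, in which case Part B patients could enter. The text does not say so, and 8.2.6 would then have no clear purpose beside 8.2.5. A third is that 8.2.6 is a leftover, since the version history records the addition of a PK analysis set section numbered 8.2.5. That is plausible but an inference; both sections are current text. Section 5.3.1 lets sample timing be adjusted, but no current schedule shows a 10 h or a Cycle 3 Day 1 sample.

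A reader might also infer more than the documents support:

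- *That the whole Part B PK dataset is discarded.* This assumes 8.2.6 overrides 8.2.5, which nothing says. Section 8.9 foresees population PK of the plasma concentrations and ties it to neither set. A set definition affects summaries and does not destroy samples.
- *That the incomplete-profile exclusion removes every Part B patient.* It is an example of a protocol deviation. A patient who gives the two planned samples has not deviated.
- *That the lack of a 10 h sample bars Part A.* It does not by itself, because the Part A profile runs to 12 h.
- *That 50 and 12 are firm counts.* Fifty is a target, and Table 2 footnote o puts it at 40-50. Twelve is the evaluable target for Part A, where non-evaluable patients are replaced, so it is no upper limit.
- *That accumulation cannot be reported.* The list definition in Section 8.8 still works for Part A.

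**Conclusion.** The point holds as a drafting error that should be corrected. The same set has two incompatible entry rules and no order of precedence. On the plain reading of 8.2.6 the Part B set is empty; under 8.2.5 it can hold all the patients that Section 5.3.2 seeks. The zero rests on reading full sampling up to 10 h as sampling that actually extends to 10 h, and on the current Part B schedule. The Cycle 3 Day 1 accumulation ratio cannot be computed in either part as written, has no stated denominator and conflicts with the definition earlier in the same section.

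The consequence is limited to descriptive secondary PK summaries. No primary endpoint and no sample size depends on it.

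**What to change.** - Keep 8.2.5 as the only PK analysis set, for both parts.
- Replace 8.2.6 by a separately named subset, such as a Part A non-compartmental set, defined by the scheduled 0-12 h profile.
- State that an incomplete PK profile means samples missing relative to the schedule for that part. Say also whether a patient who misses a scheduled sample but still meets the one-sample rule stays in the set.
- Delete the Cycle 3 Day 1 sentence in Section 8.8. Keep accumulation as Cycle 1 Day 3 or 10 divided by Cycle 1 Day 1, for Cmax and AUC(0-12), Part A only.

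The cost is a wording change in the protocol, carried into the SAP. No new samples or visits are needed. It should be settled before database lock, so that membership of the set is not chosen with the data in view.

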8.3 Methods of statistical analyses

In this open-label, Phase Ib study, no formal hypothesis testing will be conducted. Descriptive statistical and graphical displays will be employed to assess the safety and efficacy of AZD1775 monotherapy in the patient populations of interest.

A comprehensive description of the statistical analyses and data summaries for this study will be documented in a Statistical Analysis Plan (SAP) which will be finalized prior to DBL. Note that data will be presented separately for each part of the study.

The study will have a primary data cut-off for the primary analysis (see Section 9.4). Following the primary analysis data cut-off, no further statistical analysis of the data will be conducted. All safety data collected after the primary analysis and up to (and including) the last of the FPVs will be listed and/or summarised as appropriate. A CSR addendum will be prepared to include such data.

8.3.1 Demographic and baseline data

Baseline characteristics of the patients, including demography, medical history and disease characteristics will be listed for each patient and summarised by cohort.

8.3.2 Exposure

Exposure to AZD1775 (i.e. total amount of study drug received) will be listed and summarised for all patients in Part A and by expansion cohorts in Part B. Total exposure, time on study drug, and dose intensity will be summarised, along with the number and percentage of patients with at least one dose interruption and at least one dose reduction. Reason for discontinuation of study treatment will be summarised.

8.3.3 Safety analysis

In Part A DLTs will be summarised. For all parts of the study the following minimum data summaries will be presented by cohort using the Safety Analysis Set:

- TEAEs of any CTCAE grade – summarized by MedDRA preferred term and system organ class and CTCAE maximum grade
- Related TEAEs of any CTCAE grade – summarized by MedDRA preferred term and system organ class and CTCAE maximum grade
- SAEs
- Deaths summarized by primary cause
- Laboratory parameters (haematology and chemistry), vital signs, ECG data and concomitant medications including evaluations for potential DILI and QTc prolongation signals.

8.4 Efficacy

8.4.1 Objective response rate

In the expansion cohorts of Part B, the ORR (according to RECIST v1.1) will be computed and presented along with an exact 95% confidence interval (CI) using the method of Clopper and Pearson ([Clopper and Pearson 1934](#)).

8.4.2 Disease control rate

In the expansion cohorts of Part B, the DCR will be computed and presented along with an exact 95% CI using the method of Clopper and Pearson.

8.4.3 Changes in target lesion

Waterfall plots (bar charts) indicating the best percentage change from baseline in tumour size will be produced for the expansion cohorts in Part B.

8.4.4 Progression-free survival

Informational summaries and Kaplan Meier plots, without formal statistical comparisons, will be produced for expansion cohorts in Part B.

8.4.5 Duration of response

Informational summaries and Kaplan Meier plots, without formal statistical comparisons, will be produced for expansion cohorts in Part B.

8.4.6 Biomarker analysis

In Part B the number and proportion of patients having a genetic alteration in relevant tumour markers at baseline will be presented.

The relationship between clinical outcomes (ORR, DCR, DoR, and PFS) and the presence of genetic alterations in each marker will be summarised using methods appropriate for each specific clinical outcome as specified in the SAP. This analysis may be used to inform selection of TNBC and SCLC expansion cohorts in Part B.

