- Amplification of at least one of the following genes: *CCNE1*, *MYC*, *MYCL*, or *MYCN* in TNBC or SCLC

TNBC and SCLC biomarker ‘positive’ cohorts to be analysed include amplifications of *CCNE1*, *MYC*, *MYCN* or *MYCL1*.

Biomarker ‘negative’ is defined as the absence of the qualifying amplification for TNBC or SCLC as specified above. There is the potential to recruit and treat up to an additional 20 patients (total N = 50) in the TNBC and SCLC cohorts, to explore additional genetic profiles of interest or gain additional information on the existing genetic profile, based on emerging signals.

Identification of biomarkers of interest based on emerging science is anticipated as the study proceeds. Initially, a retrospective molecular analysis of tumour samples may be performed on approximately the first 15 patients under each tumour type. These patients will be allocated to the biomarker 'negative' or 'positive' cohort retrospectively, once their genetic profile analysis result is available from the central lab. To ensure balance between the biomarker-positive and biomarker-negative cohorts, a switch to prospective molecular analysis at study entry will be required after this point. A QC check of the submitted pathology material will be performed for both groups pre-treatment.

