8. STATISTICAL ANALYSIS BY ASTRAZENECA

8.1 Sample size estimate

Approximately up to 172 patients may be enrolled and treated in this study (see Figure 1): 12 in the Part A safety lead-in cohort, and a maximum of up to 160 in Part B with tumour specific cohorts (ovarian [n=60], TNBC [n=50]), and SCLC [n=50]).

Approximately 12 evaluable patients will be enrolled and treated in Part A (dose escalation). Patients must complete Cycle 1 safety evaluations and must receive at least 75% of the planned Cycle 1 dose in order to be considered evaluable. Patients receiving less than 75% of the Cycle 1 dose will be replaced unless they experience a confirmed DLT. At the end of Part A, if no safety signals are reported and the PK profile appears acceptable, the Part B tumour-specific expansion cohorts will begin enrolment.

In Part B, in the TNBC and SCLC cohorts, approximately 15 biomarker positive and 15 biomarker negative patients will be enrolled and treated. An additional 20 patients in each tumour cohort may be enrolled and treated to further explore genetic profiles of interest. In addition, 60 ovarian cancer patients will be treated. Therefore, approximately up to 172 patients may be treated in the study (Part A and Part B combined).

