8.5.2 Part B: tumour specific expansion cohorts

A formal analysis of safety and efficacy data will take place in each expansion cohort when the target number of patients have completed at least two cycles of treatment. This will include an analysis of the biomarker data in the TNBC and SCLC cohorts to inform selection of further expansion cohorts.

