8.6 Evaluation and calculation of variables by AstraZeneca or delegate

8.6.1 Calculation or derivation of efficacy variable(s)

8.6.1.1 Tumour response rate

Patients will undergo regular tumour assessments until documented objective disease progression as defined by RECIST v1.1 ([Eisenhauer et al 2009](#)). At each restaging visit the RECIST data for a patient will be assigned a response of CR, PR, SD, or PD depending on the status of the disease compared with baseline and previous assessments (see [Appendix D](#)).

The objective response rate is defined as the number of the patients with a confirmed best overall response of CR or PR divided by the number of patients in the Full Analysis Set (FAS [see Section [8.2.2](#)]). Similarly, the disease control rate is defined as the percentage of FAS patients with a best overall response of CR or PR or SD.

Progression of Target Lesions (TL) will be calculated in comparison with what the tumour burden was at a minimum (i.e., smallest sum of diameters previously recorded on study). In the absence of progression, tumour response (CR, PR, or SD) will be calculated in comparison to the baseline tumour measurements obtained before starting treatment.

If a patient has had a tumour assessment that cannot be evaluated, then the patient will be assigned a visit response of non-evaluable (NE) (unless there is evidence of progression in which case the response will be assigned as PD).

For TL measurements, if $\leq 1/3$ of the TL sizes are missing (either not evaluable or not read, or the scan was not done) then a scaling up rule will be applied as follows:

- If $\leq 1/3$ of lesions recorded at baseline are missing, then the results will be scaled up (based on the baseline sizes) to give an estimated sum of diameters and this will be used in calculations (this is equivalent to comparing the visit sum of diameters of the non-missing lesions to the baseline sum of diameters excluding the lesions that are missing and determining at what rate the lesions are changing)
- If $> 1/3$ of lesions recorded at baseline are missing, then the target lesion response will be NE. However, if the sum of non-missing target lesion diameters would result in PD (i.e., if using a value of 0 for missing lesions the sum of diameters has still increased by $> 20\%$ or more compared with the smallest sum of diameters on study and has an absolute increase ≥ 5 mm) PD takes precedence over NE.

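### If early responses decide which TNBC or SCLC profile or cohort is expanded, the pooled ORR is biased upward, and the protocol does not call for the post-selection patients to be shown separately

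*Protocol*

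**What the plan says.** - **Use of outcomes to choose expansions.** Protocol 8.4.6: "The relationship between clinical outcomes (ORR, DCR, DoR, and PFS) and the presence of genetic alterations in each marker will be summarised", followed by "This analysis may be used to inform selection of TNBC and SCLC expansion cohorts in Part B". Section 8.5.2 places this at the per-cohort analysis made once the target number of patients has completed two cycles: "This will include an analysis of the biomarker data in the TNBC and SCLC cohorts to inform selection of further expansion cohorts".
- **Sizes.** Section 8.1, for each of TNBC and SCLC: "approximately 15 biomarker positive and 15 biomarker negative patients will be enrolled and treated", then "An additional 20 patients in each tumour cohort may be enrolled and treated to further explore genetic profiles of interest". Section 7.2.2 describes "up to an additional 20 patients (total N = 50) in the TNBC and SCLC cohorts, to explore additional genetic profiles of interest", and makes this depend on emerging signals. No threshold or selection rule is given.
- **Estimator.** Section 8.6.1.1 defines ORR as confirmed responders "divided by the number of patients in the Full Analysis Set". Section 8.2.2 puts every treated patient in that set and uses it for the primary efficacy analyses. Section 8.4.1 has ORR "presented along with an exact 95% confidence interval (CI) using the method of Clopper and Pearson", with no adjustment.
- **Status of ORR.** It is a Part B primary outcome measure (2.1). The study is descriptive, without formal hypothesis testing (8.3).

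**The concern.** The patients whose responses prompt an expansion appear to be counted again in the ORR of whatever is expanded. A group picked because it did well early has, on average, done better than its true rate. Adding new patients dilutes that excess but does not remove it. A fixed-sample exact interval takes no account of the selection.

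What is at stake is how the expansion is read. A profile that looked good by chance could still look good after 20 more patients, partly because its favourable first stage is still in the numerator. The patients enrolled after the choice are the part of the data that the selection has not touched, and the protocol does not ask for them to be shown on their own.

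**Working it through.** **Inputs from the protocol.** First stage 15 + 15 = 30 per tumour type; expansion up to 20 (8.1). The size figures reproduce: 15 + 15 + 20 = 50, and 12 + 60 + 50 + 50 = 172. No precision or power basis is given for the cohort sizes, so there is none to check.

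**Assumptions, because the protocol gives none.** True ORR of 10 to 30%; no marker effect; selection rules as below. All results are exact binomial enumeration with two-sided 95% Clopper-Pearson limits. CI error means the probability that the interval misses the true ORR.

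**A. Better of two groups of 15, plus 20, pooled n = 35.** Let M be the larger of two independent Bin(15, p) counts. Pooled bias = (E[M] − 15p)/35. At p = 10%, E[M] = 2.129, so bias = (2.129 − 1.5)/35 = +1.8 points. The lower limit exceeds 10% from 8/35 upward.

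| True ORR | Bias (points) | Lower-limit error: selected (unselected) | Two-sided error: selected (unselected) |
|---|---|---|---|
| 10% | +1.8 | 3.5% (2.0%) | 3.5% (2.0%) |
| 15% | +2.2 | 2.0% (1.1%) | 2.5% (3.5%) |
| 20% | +2.5 | 2.5% (1.4%) | 2.9% (3.3%) |
| 30% | +2.8 | 2.9% (1.6%) | 3.0% (2.5%) |

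Over true ORRs from 2% to 60% the two-sided error peaks at 4.7%. The lower-limit error passes 2.5% at about 65% of those rates.

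**B. One group of 15 expanded only if it has at least 3 responses, pooled n = 35.** Conditional bias = (E[X | X ≥ 3] − 15p)/35. At p = 10%, P(X ≥ 3) = 18.4% and E[X | X ≥ 3] = 3.385. Pooled ORR averages (3.385 + 2)/35 = 15.4%, a bias of +5.4 points; CI error among expanded groups is 8.7%. At true ORR 20% the bias is +2.8 points and the error 2.3%.

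**C. A tumour type expanded only if at least 6/30 respond, N = 50.** At p = 10%, P(X ≥ 6) = 7.3% and E[X | X ≥ 6] = 6.494. Pooled ORR averages (6.494 + 2)/50 = 17.0%, a bias of +7.0 points; CI error is 23.9%. At true ORR 20% the bias is +3.0 points and the error 2.5%.

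**D. Tumour-type ORR at N = 50, expansion always done, both profiles with the same rate p.** Expected responders are 30p + 20p = 50p whichever profile receives the 20. Bias is 0 and CI error is unchanged.

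**E. Post-selection patients alone, n = 20.** Bias is 0. CI error is 1.1%, 2.2% and 2.5% at true ORR 10%, 20% and 30%.

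**The case against.** **Pooling is inferred.** No sentence says that the first 30 and the added 20 form one ORR. Section 8.5.2 speaks of further expansion cohorts and 5.5.5 of additional ones, which could be separate cohorts with their own ORR. This stands, but 7.2.2 brings the existing cohorts to 50 and 8.2.2 excludes no treated patient. One reading is free of the bias and the other is not, so the protocol should say which is meant.

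**Selection is permitted, not required.** The wording is conditional, and the extra patients may go to a profile suggested by outside science, which need not reuse any selecting responses. This stands. The bias arises only if the early responses drive the choice.

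**The study is descriptive, and association methods are left to the SAP.** Bias in an estimate does not depend on a test, but the descriptive aim limits how much the point matters. The SAP is not at hand and may add separate reporting. The denominator, the interval and the response-informed expansion are set in the protocol itself.

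**Stronger readings.** A reader might infer that the N = 50 ORR is always biased. Case D shows that it is not; bias there needs expansion to depend on response, or profile rates to differ. A reader might also infer that the CI misses more often than 5% in general. Case A shows that it does not: Clopper-Pearson is conservative enough to absorb the selection, and at true ORRs of 15% and 20% the two-sided error is lower than without selection. Larger effects from choosing among many genes need a number of profiles and prevalences that the protocol does not supply.

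**Conclusion.** The point holds in limited form. Where a profile or cohort is expanded because of its early responses and the stages are pooled, ORR is overestimated. The bias is about 2 points for the better of two profiles, with two-sided CI error still below 5%. With a go/no-go threshold and a low true rate it is larger: +5.4 points and 8.7% error in case B, +7.0 points and 23.9% in case C, both at a true ORR of 10%. At a true ORR of 20% the same thresholds give about 3 points and no excess CI error.

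These sizes rest on assumed thresholds, true rates and absence of a marker effect. They also rest on pooling, which the protocol implies but does not state. It is a worthwhile and cheap improvement to reporting, not a defect that invalidates the design.

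**What to change.** Add to 8.4.1 and 8.4.6 that, for any profile or cohort expanded after the 8.5.2 analysis, ORR with its Clopper-Pearson 95% CI is also reported in the patients enrolled after selection, beside any pooled figure. State whether the stages are pooled. If they are, label the pooled figure as including the selection data, with a CI not adjusted for selection.

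The cost is one extra table row for each expanded profile or cohort and no additional patients. The post-selection row has a wider interval: 4/20 gives 6 to 44%, against 8 to 37% for 7/35 pooled. For that reason it should stand beside the pooled estimate. Judging a profile on the 20 new patients alone would trade precision for freedom from bias, and this point does not require that.
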